10.1.2 Specific Stopping Rules for Safety

Safety data will be routinely monitored and sequential safety assessments will be conducted as subjects are enrolling to the study. The study will be stopped due to safety/toxicity concern prior to interim efficacy analysis if *any* of the following 3 stopping rules are met:

1. Liver dysfunction (clinical or laboratory [total serum bilirubin], grade 4) that does not improve to baseline or \leq grade 3 within 1 month following DEB-TACE in ≥ 7 patients (12% of 51 patients).

OR

2. Renal dysfunction (clinical or laboratory [serum creatinine], grade 3 or 4) that does not improve to baseline or \leq grade 2 within 1 month following DEB-TACE in ≥ 2 patients (1.2% of 51 patients).

OR

3. Any grade 5 AE (death) attributed as at least possibly-related to study intervention in ≥ 3 patients (4.8% of 51 patients).

The stopping rules above were used to generate the following chart, which will be adhered to with regards to stopping enrollment for the reasons of severe toxicity.

Table 4. Number of patients with defined safety/toxicity for the study to be stopped during sequential and continuous safety assessments (based on binomial distribution)

Number patients enrolled in study	3	7	11	13	17	23
Number of patients with grade 4 liver dysfunction, grade 4 renal dysfunction, or study-related death	2	4	6	7	8	9
% chance of stopping enrollment if true SAE rate is $<15\%$	94%	99%	99%	99%	99%	99%
% chance of stopping enrollment if true SAE rate is $<20\%$	90%	97%	99%	99%	99%	97%
% chance of stopping enrollment if true SAE rate is $<30\%$	78%	87%	92%	94%	90%	77%

Note: the study will also be terminated early if any of the 3 stopping rules is observed.

Adverse events grade ≥ 4 will be discussed by the interventional radiologist and medical oncologist and/or hepatologist within 1 business day of being informed of the event. If at any time a patient has a fatal complication at least possibly related to treatment, the study will immediately be put on hold. At that time, the data will be reviewed by a multidisciplinary team as to the etiology. If it is determined that the death was attributed as at least possibly-related to treatment, the study investigators will meet to discuss if the study should continue.

The patients will also be monitored for development or worsening of other recognized complications of DEB-TACE including ascites, hepatic encephalopathy, hepatorenal syndrome, biliary injury (stricture or leak), cholangitis, cholecystitis, hepatic abscess, abdominal pain, nausea, vomiting, fatigue, and fever. The study may be placed on hold or terminated based on development of these adverse events in study participants.

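### Section 10.1.2 prints Table 4's stopping probabilities inverted, leaves open whether the three safety rules run past the interim, and gives a renal trigger that does not match its benchmark

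*Combined protocol and SAP*

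**What the plan says.** Section 10.1.2, repeated in the Abstract, describes continuous monitoring ("sequential safety assessments will be conducted as subjects are enrolling to the study") and then states when the rules bind: "The study will be stopped due to safety/toxicity concern prior to interim efficacy analysis" if any one of three is met. Section 10.2 sets that interim at 17 evaluable patients, with accrual continuing.

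- Rule 1 (liver): grade 4 dysfunction not resolved "within 1 month following DEB-TACE in ≥ 7 patients (12% of 51 patients").
- Rule 2 (renal): "Renal dysfunction (clinical or laboratory [serum creatinine], grade 3 or 4) that does not improve to baseline" or to grade 2 or lower "within 1 month following DEB-TACE in ≥ 2 patients (1.2% of 51 patients").
- Rule 3 (death): grade 5 events "attributed as at least possibly-related to study intervention in ≥ 3 patients (4.8% of 51 patients").

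Table 4, said to be generated from these rules, is a chart "which will be adhered to with regards to stopping enrollment for the reasons of severe toxicity". Its event is a composite: "Number of patients with grade 4 liver dysfunction, grade 4 renal dysfunction, or study-related death". The limits are 2, 4, 6, 7, 8 and 9 events at 3, 7, 11, 13, 17 and 23 patients. Three further rows give what is labelled the chance of stopping enrollment for event rates of 15%, 20% and 30%. A note adds that any of the three rules also ends the study, without a patient range.

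Section 10.1.1 gives the benchmarks, from 166 patients treated with conventional TACE: 20 (12%) with persistent grade 4 hepatotoxicity, 2 (1.2%) with persistent grade 4 renal toxicity, and 8 (4.8%) dead within 6 weeks. It says the rules assume similar morbidity for DEB-TACE.

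**The concern.** Safety is a primary objective, so these rules must be applicable without interpretation and their stated performance must be right.

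The Table 4 rows fail on sight: at 3 patients the printed chance of stopping falls from 94% to 90% to 78% as the event rate rises from 15% to 30%. A rule that stops on excess events cannot behave that way. A reader judging the chart would believe it very likely to stop a toxic regimen early.

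The range decides outcomes. A second persistent renal event after the interim ends the study if the rules run to 51, and does not if they lapse at the interim. The text supports either reading.

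The renal rule has two further problems: its count is not derived from its benchmark in the way the other two are, and it counts a wider set of grades than the benchmark does. The death rule also counts something other than its benchmark.

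**Working it through.** **1. Table 4.** Inputs: the looks n, limits r and rates p in the table, which states a binomial basis. Printed label: P(X ≥ r). Compare with P(X < r) = 1 − P(X ≥ r).

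| n / limit | 3 / 2 | 7 / 4 | 11 / 6 | 13 / 7 | 17 / 8 | 23 / 9 |
|---|---|---|---|---|---|---|
| Printed, 15% | 94 | 99 | 99 | 99 | 99 | 99 |
| P(X < r), 15% | 93.9 | 98.8 | 99.7 | 99.9 | 99.8 | 99.6 |
| P(X ≥ r), 15% | 6.1 | 1.2 | 0.3 | 0.1 | 0.2 | 0.4 |
| Printed, 20% | 90 | 97 | 99 | 99 | 99 | 97 |
| P(X < r), 20% | 89.6 | 96.7 | 98.8 | 99.3 | 98.9 | 97.3 |
| P(X ≥ r), 20% | 10.4 | 3.3 | 1.2 | 0.7 | 1.1 | 2.7 |
| Printed, 30% | 78 | 87 | 92 | 94 | 90 | 77 |
| P(X < r), 30% | 78.4 | 87.4 | 92.2 | 93.8 | 89.5 | 77.1 |
| P(X ≥ r), 30% | 21.6 | 12.6 | 7.8 | 6.2 | 10.5 | 22.9 |

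All 18 printed cells reproduce as P(X < r) within 1 point; none reproduces as P(X ≥ r). Carrying the event count forward exactly from look to look, the chance of stopping at any of the six looks is 6.8%, 13.2% and 37.9% at 15%, 20% and 30%. These are for the Table 4 limits alone, without the three concurrent rules.

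**2. Range.** Inputs: counts 7, 2 and 3 (section 10.1.2); rates 12%, 1.2% and 4.8% (section 10.1.1). For each rule, P(X ≥ count) with X binomial(N, rate). For any rule under independence, 1 − (1 − a)(1 − b)(1 − c).

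| N | Liver ≥ 7 | Renal ≥ 2 | Death ≥ 3 | Any rule |
|---|---|---|---|---|
| 17 | 0.2% | 1.7% | 4.5% | 6.4% |
| 23 | 1.5% | 3.1% | 9.6% | 13.7% |
| 51 | 41.4% | 12.5% | 44.6% | 71.6% |

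For N = 51: 1 − 0.586 × 0.875 × 0.554 = 0.716. At assumed lower rates (liver, renal, death) the 51-patient figure is 28.6% for 8%, 1.2%, 2%, and 14.9% for 5%, 1.2%, 1%. The 37 DEB-TACE patients in section 1.2 had no irreversible grade 4 bilirubin or grade 3–4 creatinine event and no treatment-related death. The one-sided 95% upper limit for 0 of 37 is 1 − 0.05^(1/37) = 7.8%, so those data allow the lower rates. Irreversible there means at least 6 weeks, not the rules' 1 month.

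**3. Brackets.** Benchmark × 51: liver 0.12 × 51 = 6.12, rounded up to 7; death 0.048 × 51 = 2.45, rounded up to 3; renal 0.012 × 51 = 0.61, which rounds up to 1, not 2. The source of 1.2% is 2/166. The trigger fractions are 7/51 = 13.7%, 2/51 = 3.9% and 3/51 = 5.9%.

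**4. Events.** Renal: rule 2 counts grade 3 or 4; section 10.1.1 and Table 4 count grade 4. Rule 2 is met by patient 51 with probability 12.5% at 1.2%. The grade 3–4 rate is not given; at assumed rates of 2%, 3% and 5% the probability is 27%, 45% and 73%. Death: the benchmark is mortality at 6 weeks; rule 3 counts deaths at least possibly related, with no window.

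**The case against.** Much can be said for the plan, and several stronger readings should be resisted.

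- A reader might infer three rival ranges: 17, 23 and 51. The documents do not support that. Twenty-three is only where the separate composite in Table 4 ends. Accrual continues, and response imaging follows the last of up to four procedures, so more than 17 patients may be enrolled at the interim. The real ambiguity is interim versus 51, and the 6% figure is the low end of the interim reading.
- A reader might see section 12.2, which calls the review after patient 17 final, as contradicting section 9.1, which puts the final safety analysis after 51. Under its interim-analysis heading, 12.2 reads naturally as closing the interim review.
- A reader might call rule 1's reliance on bilirubin a mismatch with the broader hepatotoxicity benchmark. Section 10.1.1 explains the choice: persistent hyperbilirubinemia predicted death or urgent transplant better than transaminitis.
- A reader might take 72% as the trial's actual chance of stopping. It applies the benchmarks to events that they do not exactly measure, and it assumes independence. It shows sensitivity to range and is not a forecast.
- A reader might infer that a third related death after the interim goes unchecked. Section 10.1.2 puts the study on hold at any possibly related death, whenever it occurs; only automatic termination differs. Discretionary termination and DSMC review also continue.
- Table 4's limits, which govern stopping, are not affected by the mislabelled rows.

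What stands after all this: the inverted probabilities, the unresolved range, the renal count and the unmatched renal and death definitions.

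**Conclusion.** The point holds and should be fixed. The Table 4 inversion is certain: it follows from the table's own inputs and rests on no outside assumption. The conflict over range is in the text. Its size depends on the true rates: about 6% by 17, 14% by 23 and 72% by 51 at the benchmark rates with independent events, and about 15–29% by 51 at the assumed lower rates. On any of these, the same counts give very different protection depending on the range. The renal bracket is arithmetically inconsistent with its count, although the operative trigger of 2 patients is itself clear. The renal grade mismatch is plain on the page; its effect cannot be sized without the historical grade 3–4 rate. The death mismatch is also plain, and softened by the hold after any related death.

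**What to change.** Amend section 10.1.2, the Abstract and, for one phrase, section 12.2:

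- Replace the Table 4 probabilities with their complements, or relabel the rows as chances of not stopping. State that they are per look, and add the cumulative figures.
- State one patient range for the three rules and make section 10.1.2, the Abstract and the Table 4 note agree. Say in section 12.2 that the review after patient 17 is the interim review.
- Give the stopping probabilities over that range at the benchmark rates and at an unacceptable rate set by the sponsor.
- Word all three brackets as historical benchmark rates, and give the trigger fractions (13.7%, 3.9% and 5.9% of 51) separately. Explain how the renal count was chosen.
- Reconcile the renal grade and the death definition across section 10.1.1, the rules and Table 4. The clinical definitions and thresholds are the sponsor's to choose.

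The cost is statistician time and one amendment, possibly with a re-tabulation of the sponsor's 166-patient cohort to obtain rates for the events actually counted. No extra patients or assessments are needed.

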Secondary Objectives	
• To measure overall radiographic response (by RECIST v1.1 and mRECIST) 6 months after the date of the first planned DEB-TACE procedure.• To measure time to untreatable progression (TTUP). TTUP is defined as time to disease progression untreatable by liver-directed percutaneous or surgical methods.• To measure median time to progression (TTP)• To measure hepatic progression free survival (HPFS)• To measure progression free survival (PFS)• To measure overall survival (OS)• To determine the proportion of patients who remain active on the wait list for a liver transplant and eventually are transplanted.• To determine the proportion of patients who are inactivated or drop out from the wait list for any reason but transplantation.• To determine the proportions of patients who are successfully down-staged and achieve active waitlist status and eventually are transplanted.• To measure proportion with alpha-fetoprotein (AFP) response with $\geq 50\%$ decline from baseline (in patients with baseline level ≥ 20) post DEB-TACE and test for association with hepatic and overall response rate, PFS, and OS• To determine whether cardiac function changes occur as a result of DEB-TACE with doxorubicin• To obtain pharmacokinetic data for doxorubicin administered as a part of DEB-TACE procedures

Abstract

Study Design	Prospective open-label two-stage phase II clinical trial to evaluate the safety and efficacy of DEB-TACE in patients with liver-only HCC and significant hepatic dysfunction who are being considered for a liver transplant.
Number of patients	17 patients will be enrolled into the first stage of the study for safety and efficacy 34 patients will be enrolled into the second stage of the study
Duration of Therapy	Most patients will need only one DEB-TACE treatment, performed within 60 days of Screening procedures For patients that have more than one treatment, the procedure will be done about 4 weeks after the first, or previous treatment, up to 4 treatments total
Duration of Follow up	Post Treatment Evaluation will last 1 year
Duration of study	The study will reach completion 5 years from the time the study opens to accrual

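### Table 4 counts patients enrolled where its binomial calculation needs patients with known outcomes, so its limits stop less often, and later, than that calculation implies

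*Combined protocol and SAP*

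**What the plan says.** Section 10.1.2 gives three fixed-count rules: 7 patients with liver dysfunction, 2 with renal dysfunction, and 3 deaths at least possibly related to treatment. The liver and renal rules count a patient only if the toxicity has not improved within 1 month of DEB-TACE. The section then says: "The stopping rules above were used to generate the following chart, which will be adhered to with regards to stopping enrollment". That chart, Table 4, is described as binomial and meant for sequential and continuous use. Its columns are headed "Number patients enrolled in study" (3, 7, 11, 13, 17, 23), with limits of 2, 4, 6, 7, 8 and 9. The events counted are "Number of patients with grade 4 liver dysfunction, grade 4 renal dysfunction, or study-related death". This row carries no 1-month condition.

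On timing, Section 10.1.2 says "Safety data will be routinely monitored and sequential safety assessments will be conducted as subjects are enrolling to the study". Section 12.2 lets accrual continue during the interim analyses. The Abstract says "Most patients will need only one DEB-TACE treatment, performed within 60 days of Screening procedures". Under the intention-to-treat exceptions in Section 12.3, some enrolled patients are never treated and are replaced. By contrast, the 17-patient safety look in Section 12.2 counts patients who have received DEB-TACE and had potential for at least 4 weeks of follow-up.

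**The concern.** A binomial limit of r events in n patients has its calculated properties only if all n outcomes are known. Counting enrolled patients puts people in the denominator who cannot yet have contributed an event. When an early event is finally classified, enrolment may have passed into the next column, where a higher limit applies. The table then stops less often than the calculation behind it.

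This matters most early. The fixed liver rule needs 7 patients, so before that point Table 4's lower limits (2, 4 and 6) are the only numerical stop for liver toxicity. Liver toxicity is also the most frequent of the three in the retrospective conventional-TACE series on which the rules were based (12%, against 1.2% renal and 4.8% mortality, Section 10.1.1).

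**Working it through.** **1. Reproduce Table 4.** With n the column number and r the limit, P(X < r) for X ~ Binomial(n, p) matches all 18 printed percentages to within 1 point. At p = 0.30 it gives 78.4, 87.4, 92.2, 93.8, 89.5 and 77.1%, against the printed 78, 87, 92, 94, 90 and 77%. So each calculation treats all n enrolled patients as having known outcomes. (These are chances of *not* reaching the limit, although the rows are labelled as chances of stopping. That is a separate error, and relabelling would not cure this one.)

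**2. One look, no accrual assumption.** Take the limit of 4 at 7 enrolled, p = 0.30. The chance of reaching it is P(X ≥ 4):

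| Of 7 enrolled, outcome known | P(X ≥ 4) |
|---|---|
| 7 | 0.126 |
| 6 | 0.071 |
| 5 | 0.031 |
| 4 | 0.008 |

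**3. How many are pending.** The accrual rate is not stated. From the 5-year duration, 51/60 = 0.85 per month. Allowing a year for follow-up, 51/48 = 1.06 per month. The enrolment-to-treatment interval is not stated either, so I take from none up to 0-2 months. With 1 month to classify, the lag is 1 to 3 months. That leaves about 0.85 × 1 = 0.9 to 1.06 × 3 = 3.2 patients pending. Columns are 2 to 6 patients apart, so a limit can rise before events are known, but need not.

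**4. Chance that Table 4 alone ever stops.** Simulation with Poisson accrual, uniform wait to treatment, every event classified 1 month after treatment, and the next column's limit applying between columns:

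| Accrual, wait | True rate | n = enrolled | n = followed 1 month |
|---|---|---|---|
| 0.85/month, none | 30% | about 31% | about 38% |
| 1.06/month, 0-0.5 month | 30% | 26% | 38% |
| 1.06/month, 0-2 months | 30% | 21% | 35-38% |
| 1.06/month, 0-2 months | 50% | 83% | 93% |
| 2/month, 0-2 months | 30% | 11% | 37% |

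If the table is consulted only when enrolment reaches a column (1.06/month, 0-2 months, 30%), the figures are 15% against 38%.

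**5. Whole safety stop.** Add the three fixed-count rules, active throughout. Events are split 12 : 1.2 : 4.8 (liver : renal : death), with deaths known within a month:

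| Accrual, wait | True rate | Stops: enrolled vs followed | Mean enrolled at stop |
|---|---|---|---|
| 0.85/month, 0-0.5 month | 30% | 99% vs 99% | 23.1 vs 21.1 |
| 1.06/month, 0-2 months | 30% | 99% vs 99% | 24.7 vs 21.7 |
| 1.06/month, 0-2 months | 50% | 100% vs 100% | 13.3 vs 10.1 |
| 2/month, 0-2 months | 30% | 99% vs 99% | 27.3 vs 23.1 |
| 2/month, 0-2 months | 50% | 100% vs 100% | 16.4 vs 11.5 |

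**6. If the fixed rules lapse.** Section 10.1.2 introduces them as applying before the interim efficacy analysis. At a 30% liver rate, P(7 or more of 17) = 22.5%. A liver-only run (Table 4 plus the 7-patient rule, lapsing after 17 classified patients) stops in 27% (enrolled) against 41% (followed) at 30%, and 63% against 72% at 40%.

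**The case against.** The strongest reply is that Table 4 is not the whole safety stop. The fixed-count rules do not depend on enrolment, and a note under Table 4 keeps them in force beside it. A possibly related death puts the study on hold at once. Section 12.2 also applies the toxicity criteria to 17 treated patients with follow-up. This stands. A reader might infer that the safety stop can fail altogether, but step 5 does not support that while the fixed rules are active.

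Second, Table 4's event row has no 1-month condition, and laboratory tests are due at days 1 and 7±4. If grade 4 events count at once (known within about 11 days, 1.06/month), the enrolled version stops in about 37% of trials at a 30% rate when patients are treated at enrolment, and 32% with a 0-12 day wait. Against about 38% for full follow-up, the loss is 1-6 points. This stands as a reading, but the section also says that the chart was generated from rules that do carry the condition. Untreated patients inflate n under either reading.

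Third, a reader might take the Abstract to mean that enrolled patients wait up to 60 days. Those 60 days run from screening, so the 0-2 month wait is my assumption at the long end. A reader might also infer that every limit has always risen before its events are known. At about one patient per month it often has not. If each column means the first n patients enrolled, the limit would not lapse at all. The protocol does not say which reading is meant.

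**Conclusion.** The denominator does not match the calculation behind it, and it differs from the one that the protocol uses for its own 17-patient look. With the next column's limit applying between columns and a 1-month classification delay, Table 4 alone loses about 7 to 17 percentage points of stopping probability at a true 30% rate for accrual of 0.85-1.06 per month. The loss is larger at faster accrual and smaller if grade 4 events count at once.

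For the safety stop as a whole, the documents support delay rather than failure, provided that the fixed rules remain active: about 2-3 more patients enrolled at about 1/month, and 4-5 at 2/month. If those rules lapse at the interim efficacy analysis, the backstop is weaker and the loss in Table 4 matters more. All simulated figures rest on the assumed accrual rate, treatment wait and event split.

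**What to change.** - Index Table 4 by patients treated who have completed 1 month after first DEB-TACE or have already had a stopping event.
- State which limit applies between columns.
- Reconcile the Table 4 event row with rules 1 and 2 on whether the 1-month persistence condition applies. The renal grades also differ (3 or 4 in rule 2, 4 in the table) and must be reconciled.
- State whether the fixed-count rules continue after the interim efficacy analysis.
- Recompute the probability rows on the new denominator, including the chance of stopping at an acceptable rate.

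The cost is the wording of one table, a running tally and a recalculation, with no extra patients or visits. There is a small statistical price. At a true 15% rate and 0.85-1.06 patients per month, the chance that Table 4 stops the study rises from about 2-5% to about 6-8%. It rises to about 8-11% if events count at once, because events then enter the count before non-events do.

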2.0 OBJECTIVES

Primary Objective

- To determine the safety of DEB-TACE in patients with HCC confined to liver who are being considered for liver transplantation
- To determine the response rate to DEB-TACE by conventional and modified Response Evaluation Criteria in Solid Tumors (RECIST version 1.1, mRECIST [22]) for treated lesions in patients with liver-only HCC who are being considered for liver transplantation.

Secondary Objectives

- To measure overall radiographic response (by RECIST v1.1 and mRECIST) 6 months after the date of the first planned DEB-TACE procedure. To measure time to untreatable progression (TTUP). TTUP is defined as time to disease progression untreatable by liver-directed percutaneous or surgical methods.
- To measure median time to progression (TTP)
- To measure hepatic progression free survival (HPFS)
- To measure progression free survival (PFS)
- To measure overall survival (OS).
- To determine the proportion of patients who remain active on the wait list for a liver transplant and eventually are transplanted.
- To determine the proportion of patients who are inactivated or drop out from the wait list for any reason but transplantation.
- To determine the proportions of patients who are successfully down-staged and achieve active waitlist status and eventually are transplanted.
- To measure proportion with alpha-fetoprotein (AFP) response with $\geq 50\%$ decline from baseline (in patients with baseline level ≥ 20) post DEB-TACE and test for association with hepatic and overall response rate, PFS, and OS.
- To determine whether changes in cardiac function occur as a result of DEB-TACE with doxorubicin
- ***To obtain pharmacokinetic data for doxorubicin administered as a part of DEB-TACE procedures***

Exploratory/Other Objectives

- To describe treatment response by histopathology at the time of liver transplantation (in the subgroup of patients who undergo LT).

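### Table 4 labels the chance of not reaching the safety boundary as the chance of stopping enrollment

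*Combined protocol and SAP*

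**What the plan says.** Safety is a primary objective (section 2.0): "To determine the safety of DEB-TACE in patients with HCC confined to liver who are being considered for liver transplantation". Section 10.1.2 lists three separate stopping rules, then gives a chart "which will be adhered to with regards to stopping enrollment for the reasons of severe toxicity".

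The title of that chart, Table 4, reads "Number of patients with defined safety/toxicity for the study to be stopped during sequential and continuous safety assessments (based on binomial distribution". Its trigger row is the "Number of patients with grade 4 liver dysfunction, grade 4 renal dysfunction, or study-related death". The counts are 2, 4, 6, 7, 8 and 9 at 3, 7, 11, 13, 17 and 23 patients enrolled, so stopping means reaching or exceeding the listed count.

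Three further rows begin with a percent sign and "chance of stopping enrollment if true SAE rate is", followed by <15%, <20% or <30%. They hold the chart's stated performance:

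| True rate | n=3 | 7 | 11 | 13 | 17 | 23 |
|---|---|---|---|---|---|---|
| <15% | 94 | 99 | 99 | 99 | 99 | 99 |
| <20% | 90 | 97 | 99 | 99 | 99 | 97 |
| <30% | 78 | 87 | 92 | 94 | 90 | 77 |

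Two other controls run alongside the chart. A note says "the study will also be terminated early if any of the 3 stopping rules is observed", and after a fatal complication at least possibly related to treatment "the study will immediately be put on hold".

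**The concern.** A rule that stops when too many patients have events must stop more often as the true event rate rises. The printed rows do the reverse: reading down the first column, the stated chance falls from 94% to 90% to 78%. The rows cannot be cumulative either. The 30% row drops from 94% at 13 patients to 77% at 23, and the probability of having stopped cannot go down as enrollment continues.

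These rows are the only operating characteristics the plan gives for its safety stopping. The 30% row bears most on detecting excess toxicity. The historical rates in section 10.1.1 are 12% persistent grade 4 hepatotoxicity, 1.2% persistent grade 4 renal toxicity and 4.8% mortality. They sum to 18% even if no patient had more than one. Someone reading 90% at 17 patients in the 30% row would think the chart nearly always stops a treatment that is clearly too toxic.

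**Working it through.** **Inputs, all from Table 4.** Looks (n, k): (3, 2), (7, 4), (11, 6), (13, 7), (17, 8), (23, 9). Rates p = 0.15, 0.20, 0.30, reading each < sign as the point value. X is Binomial(n, p).

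**Step 1: reproduce the printed figures.** The formula that fits is P(X ≤ k−1), the chance of not reaching the count at a single look. By hand for n=3, k=2, p=0.30: 0.7³ + 3(0.3)(0.7²) = 0.343 + 0.441 = 78.4%, printed as 78.

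| P(X ≤ k−1), % | n=3 | 7 | 11 | 13 | 17 | 23 | Largest gap from print |
|---|---|---|---|---|---|---|---|
| p=0.15 | 93.9 | 98.8 | 99.7 | 99.9 | 99.8 | 99.6 | 0.87 point |
| p=0.20 | 89.6 | 96.7 | 98.8 | 99.3 | 98.9 | 97.3 | 0.40 point |
| p=0.30 | 78.4 | 87.4 | 92.2 | 93.8 | 89.5 | 77.1 | 0.46 point |

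All 18 cells match; the 0.87 gap is 99.87% shown as 99%. P(X ≥ k), P(X > k), P(X ≤ k) and the cumulative crossing probability do not reproduce the table.

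**Step 2: single-look chance of reaching the count**, P(X ≥ k) = 1 − P(X ≤ k−1).

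| P(X ≥ k), % | n=3 | 7 | 11 | 13 | 17 | 23 |
|---|---|---|---|---|---|---|
| p=0.15 | 6.1 | 1.2 | 0.3 | 0.1 | 0.2 | 0.4 |
| p=0.20 | 10.4 | 3.3 | 1.2 | 0.7 | 1.1 | 2.7 |
| p=0.30 | 21.6 | 12.6 | 7.8 | 6.2 | 10.5 | 22.9 |

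**Step 3: cumulative chance that the chart alone has stopped the study.** The title describes continuous assessment, but the plan does not say which count governs between columns, for example at patients 4 to 6. An exact patient-by-patient recursion gives two answers.

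*Reading A:* the chart is checked only at the six sizes. The totals are the same if each count applies back from its listed n, because a count reached earlier is still met at that n.

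| Reading A, % | n=3 | 7 | 11 | 13 | 17 | 23 |
|---|---|---|---|---|---|---|
| p=0.15 | 6.1 | 6.5 | 6.6 | 6.6 | 6.6 | 6.8 |
| p=0.20 | 10.4 | 11.5 | 11.8 | 11.8 | 12.1 | 13.3 |
| p=0.30 | 21.6 | 25.6 | 27.0 | 27.5 | 30.0 | 37.9 |

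*Reading B:* each count applies from its listed n until the next column (2 events at patients 3–6, 4 at 7–10, 6 at 11–12, 7 at 13–16, 8 at 17–22, 9 at 23).

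| Reading B, % | n=3 | 7 | 11 | 13 | 17 | 23 |
|---|---|---|---|---|---|---|
| p=0.15 | 6.1 | 22.4 | 22.8 | 22.8 | 22.9 | 23.1 |
| p=0.20 | 10.4 | 34.5 | 35.6 | 35.6 | 35.7 | 36.6 |
| p=0.30 | 21.6 | 58.0 | 60.6 | 60.6 | 61.4 | 65.5 |

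Hand check of reading B by patient 7 at p=0.15: the chance of at least 2 events in 6 patients is 1 − 0.85⁶ − 6(0.15)(0.85⁵) = 22.4%. A simulation of 400,000 trials gave 23.0, 36.5 and 65.4% by patient 23.

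Under both readings the chance of stopping rises with the true rate, opposite to the printed rows.

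**The case against.** The arithmetic is not in dispute, but four points can be made for the plan.

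- **No action changes.** The chart binds through its counts, and the percentage rows trigger nothing. Enrollment would stop at the same patient with either label. This stands. The harm falls on whoever judges the boundary by these rows.
- **A benign reading exists.** With the < signs, the numbers fit a statement of protection against stopping wrongly, with the word *not* missing. Low stopping at 15% and 20% may well be intended. That may explain the error, but nothing in the document defines the rows that way, and at 30% a high chance of not stopping is no reassurance.
- **The chart is not the only safeguard.** This also stands, and chart-alone figures understate the whole plan. As an illustration, scale the section 10.1.1 rates by 30/18 to 20% liver, 2% renal and 8% death. Treat the types as mutually exclusive and all deaths as related, apply the three rules throughout, and check the chart at the six sizes. By patient 23 the three rules alone stop about 46% of trials, and rules or chart about 56%. At least one death, and so a hold, occurs in 1 − 0.92²³, about 85%. By patient 17 the figures are about 22%, 40% and 76%. These rest on an assumed split of events and do not make the printed rows correct.
- **The between-column rule is a separate matter.** It is, and reading B is only one interpretation. It is raised because no cumulative figure can be given until the rule is stated.

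**Conclusion.** The concern holds. All 18 entries are single-look probabilities of not reaching the boundary, printed as probabilities of stopping. At a true rate of 30% the stated 77–94% should be 6.2–22.9% per look. The cumulative chance by patient 23 for the chart alone is 37.9% under reading A or 65.5% under reading B. At 15% and 20% it is 6.8% and 13.3%, or 23.1% and 36.6%.

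These figures assume independent patients with a common event rate, taken at exactly 15%, 20% or 30%, and exclude the three parallel rules and the hold after a related death. The trigger counts themselves are not shown to be wrong. What is wrong is the stated performance of a binding safety chart in a trial with safety as a primary objective, so the correction is needed before anyone relies on those rows.

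**What to change.** 1. Relabel the three rows as the single-look chance of not reaching the boundary; the < signs then read as *at least*, to rounding. Alternatively, replace the entries with the P(X ≥ k) values from step 2 at exact rates.
2. State which count applies between the listed sample sizes, and add the cumulative row for that reading from step 3.
3. Note under the table that the figures cover the chart alone. The stopping added by the three rules and the hold depends on event rates by type, which the plan does not fix for this trial; any range shown should state its assumptions.
4. Have the sponsor and the DSMC re-confirm the boundary against the corrected figures. No new boundary is proposed here.

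A secondary point, for reconciliation within section 10.1.2: the lead-in says "The study will be stopped due to safety/toxicity concern prior to interim efficacy analysis" if any of the three rules is met, while the note under Table 4 carries no such time limit. The text should say whether those rules apply throughout, and whether the chart applies after patient 23.

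The cost is a corrected table, one sentence on the between-column rule and one note, in an amendment. No patients or procedures are added. The drawback is that the stated safety performance becomes less favourable.
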